##### ***Secondary outcomes:***

**1. Retraction rate:** to assess the antero-posterior movement of anterior teeth and first molars, the principle investigator will take study models for every participant monthly during the follow up visits. Then will digitize the models and identify the landmarks, reference lines and planes on the pre, interim and post-retraction digital dental models for measurements reading. Also, by identifying the landmarks, reference lines and planes using CBCT taken before and after the completion of retraction.

**2. Pain:** each patient will fill a questionnaire regarding his treatment experience in a Visual Analog Scale (VAS) scoring from 1-10 by making a handwritten mark on a 10-cm line that represents a continuum between “no pain” on the left end (0 cm) of the scale and the “worst pain” on the right end of the scale (10 cm). The questionnaire will include several questions related to oral hygiene, pain and discomfort experienced throughout the trial.

**3. Root resorption:** will be accessed by the principle investigator via CBCT taken before and after the completion of retraction. The resorption will be identified using

scoring system of Levander and Malmgren that classifies it into 5 grades: 0, no root resorption; 1, mild resorption, with the root of normal length and only an irregular contour; 2, moderate resorption, with small areas of root loss and the apex having an almost straight contour; 3, severe resorption, with loss of almost one third of root length; and 4, extreme resorption, with loss of more than one third of the root length.

**4. *Anterior teeth torque:*** will be accessed by the principle investigator via CBCT taken before and after the completion of retraction. The principal investigator will identify the landmarks, reference lines and planes, then will interpret the measurements in degrees.

**5. *Anterior teeth extrusion/intrusion:*** will be accessed by the principle investigator via CBCT taken before and after the completion of retraction. The principal investigator will identify the landmarks, reference lines and planes, then will interpret the measurements in millimeters.

**6. *Anterior teeth tip:*** will be accessed by the principle investigator via scanned digital models taken before and after the completion of retraction.

**7. *Molar Rotation:*** will be accessed by the principal investigator via digitalized dental models. These records will be taken before and after the completion of retraction by identifying the landmarks, reference lines and planes, then will interpret the measurements of the angles in degrees.

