## C] Interventions:

➤ **Medical History Questionnaire:**

For every patient, to exclude the presence of any systemic condition interfering with orthodontic treatment.

➤ **Clinical Examination:**

Oral structures will be examined to identify caries, fracture or missing teeth. Gingival tissues will be carefully examined for any gingivitis, periodontitis, recession, or lesions.

> **Diagnosis**

Check the potential patient to fulfill the previously mentioned inclusion criteria. Every participant will be asked to sign an informed consent about the study. Full set of records (study models, panorama radiograph and lateral cephalometric radiographs, photos) will be taken for every patient as part of the routine procedure for treatment of patients in the clinic of the Orthodontics and Dentofacial Orthopedics Department, Future University in Egypt.

> **Clinical Procedure:**

After taking pre-treatment records, every patient will receive:

- Bonding of all teeth except for first premolars and banding/bonding the first and second molars will be done using Roth prescription brackets (0.022 x 0.028 slot)\*.
- Miniscrews will then be placed in the upper arch between the second premolar and first molar\*\*.
- The patient will be referred for extraction of first premolars.
- Anchorage will be secured, followed by Leveling and alignment for the bonded and banded teeth through following the wire sequence: 0.014 Nitti, 0.016×0.022 Nitti and 0.017×0.025 StSt.

- After levelling and aligning is completed (right before retraction), the patient will be referred for the uptake of pre-intervention records:
  - a- CBCT
  - b- Impression and models
  - c- photo (Extraoral & Intraoral)
  - d- pain questionnaire

➢ **Acquisition of pre-intervention records:**

- The patient will be referred for the uptake of a CBCT, which are considered to be the T0 records.
- Impressions will be taken before retraction (without the archwire in place) followed by digital scanning of produced models.
- Photos (Extraoral & Intraoral)
- Pain questionnaire distributed with explanatory session on it

➢ **Beginning of Retraction:**

*Frictionless group:*

- A braided ligature wire extended between the second premolars and miniscrews will be used for proper indirect anchorage control.
- Closing retraction T-loops will be fabricated using 0.017 x 0.025 TMA wire. The loop will be positioned halfway the extraction space and the canine. [40,41].
- A gable angle of 45° will be added to the posterior segment.

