## D] Outcomes

[figure not shown]
**Primary outcome:** is to monitor the anchorage loss during “En-masse retraction”. All outcomes will be assessed as the difference between T0 at the start of retraction and T1 after complete space closure.

**Secondary outcomes:** is to monitor the changes in the anterior teeth position (final anterior teeth tip, torque and vertical position), rate of space closure, presence of any root resorption and pain associated with the different methods used for retraction.

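### Root resorption is a 0–4 grade with no stated reference length and no limit between grades 2 and 3, so its T0–T1 difference is ambiguous and insensitive; the two planned CBCTs would give root shortening in mm

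*Protocol*

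**What the plan says.** Protocol, III) A] Data collection methods, secondary outcome 3, has root resorption read "via CBCT taken before and after the completion of retraction" on a five-grade published index. Grade 0 is no resorption. The other grades are:

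- Grade 1, a shape criterion: an uneven outline on a root that has kept its length.
- Grade 2, also mainly a shape criterion, is worded "2, moderate resorption, with small areas of root loss and the apex having an almost straight contour".
- From grade 3 upwards the scale turns to proportions of length. Grade 3 is worded "3, severe resorption, with loss of almost one third of root length".
- Grade 4 covers any loss beyond a third.

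Protocol, D] Outcomes, sets how change is formed: "All outcomes will be assessed as the difference between T0 at the start of retraction and T1 after complete space closure".

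Protocol, C] Interventions, fixes the timing. Under the pre-intervention records: "The patient will be referred for the uptake of a CBCT, which are considered to be the T0 records". These come once the teeth are levelled and aligned. The radiographs listed before that point are a panoramic film and lateral cephalograms. No root length in mm is planned as an outcome.

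**The concern.** The Introduction names root resorption as an adverse effect of uncontrolled tooth movement, and the trial compares two mechanics on it. A before–after comparison needs a scale whose steps mean the same at both times and which moves when the root shortens. Two features of the wording work against that.

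1. Grades 3 and 4 need an original root length, and none is named. At T0 no earlier CBCT exists to supply it.
2. Grade 2 ends at a small loss and grade 3 begins at nearly a third. Nothing says where a loss between the two belongs.

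If the arms differ in shortening of an intermediate size, both could receive the same grade, or grades that depend on the reader. The report could then show no difference in a harm because the scale was too coarse to show one. The issue is what is measured, not which test is applied to it.

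**Working it through.** **The plan's own figure.** The protocol gives no calculation for root resorption. Its only one, in F] Sample size calculation, uses SD 0.76, difference 1.0, power 0.8 and alpha 0.05 (two-sided assumed): n = 2 × (1.96 + 0.84)² × 0.76² / 1.0² ≈ 9.1, rounded up to 10 per arm. This matches the stated 10 (the t-test version gives 10.1). It concerns another variable and does not bear on this point.

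**Step 1: what each grade needs.** Grade 0 is absence of resorption. Grade 1 requires normal length and an irregular contour. Grade 2 is a small loss with a flattened apex. These can mostly be judged on a single image. Grades 3 and 4 are proportions, (reference length − present length) / reference length, and need a reference.

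**Step 2: what the T0–T1 difference then means.** Three readings are open:

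- *Both scans graded against the original root.* For grades 3 and 4 at T0, the reference can come only from panoramic or cephalometric films. The protocol's own literature review (CBCT, part c) reports that panoramic films underestimated apical resorption.
- *T1 graded only for loss since the T0 scan.* The T1 grade is then already the change, and subtracting a T0 grade distorts it. A tooth graded 2 at T0 with no further loss would score 0 − 2 = −2, an apparent improvement.
- *Each scan graded alone on shape.* A tooth at grade 2 at T0 that shortens further, but by clearly less than a third, can stay at grade 2 and record 2 − 2 = 0.

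**Step 3: where the gap lies.** Root lengths are assumed; the protocol gives none. Percentage loss = loss / root length.

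| Assumed root (mm) | One third (mm) | 1 mm loss | 2 mm loss | 3 mm loss |
|---|---|---|---|---|
| 11 | 3.7 | 9.1% | 18.2% | 27.3% |
| 13 | 4.3 | 7.7% | 15.4% | 23.1% |
| 15 | 5.0 | 6.7% | 13.3% | 20.0% |
| 17 | 5.7 | 5.9% | 11.8% | 17.6% |

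A 2 mm loss is 12% to 18% of the root, well short of a third and arguably more than grade 2 describes. A 1 mm loss might be read as grade 2, and 3 mm on the shortest root as grade 3. The edges of the gap cannot be fixed from the text.

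**Step 4: what it could cost.** This is a simulation on assumed inputs (2,000 runs per row): one root of 13 mm per patient, 15 per arm, mean loss 1.0 versus 1.8 mm, SD 0.7, losses truncated at zero, no reading error added. Grade 0 is a loss below 0.3 mm, grade 1 is below 4% (0.04 × 13 = 0.52 mm), grade 2 runs up to the limit shown, grade 3 up to one third, and grade 4 is above that. Loss is counted from T0, so the T0 reference problem is left out. The test is a t-test on mm and Mann–Whitney on grades.

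| Grade 3 starts at | Power, mm | Power, grade | Difference | Patients in grade 2 |
|---|---|---|---|---|
| 12% (1.56 mm) | 0.854 | 0.756 | 0.10 | 44% |
| 15% (1.95 mm) | 0.859 | 0.708 | 0.15 | 61% |
| 20% (2.60 mm) | 0.857 | 0.545 | 0.31 | 79% |
| 30% (3.90 mm) | 0.866 | 0.369 | 0.50 | 86% |

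The mm column varies only by simulation error. The grade column falls because of where the unstated limit is placed.

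**The case against.** A reader might go further and infer that no T0 grade can be derived and that loss during retraction is largely unmeasured. The documents do not support either. Grades 0 to 2 can mostly be scored on the T0 image alone. Previous orthodontic treatment is an exclusion and T0 follows levelling only, so T0 grades of 3 or 4 may be uncommon, though the protocol gives no frequency. At T1 the T0 CBCT is available as a reference. The remark about panoramic films says they underestimate resorption, not that they cannot give a rough length.

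Other points in the plan's favour:

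- The subtraction rests on one general sentence that also covers pain and rate of closure, and the same section describes this outcome as the presence of any resorption. A statistical analysis plan could refine how the grade change is formed.
- The index is published and may set limits that the protocol's paraphrase omits. That cannot be checked here. The data collection section cites reference 34, which the reference list gives as a CBCT versus periapical comparison; the outcome table cites reference 39.
- Two blinded assessors, training and kappa are planned.
- The mm ranges above rest on assumed root lengths and losses.

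These points limit the concern to ambiguity and insensitivity, but do not remove it. The reference length and the grade 2/3 limit belong to the measurement itself, which the protocol defines. Reader agreement can expose inconsistent grading but does not supply the missing limit, and two readers may agree on a grade that does not move.

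**Conclusion.** The point stands in this form: the grade has no stated reference length for grades 3 and 4, its worded steps leave intermediate losses without a grade, and its T0–T1 difference is therefore ambiguous and insensitive to root shortening during retraction. The outcome is coarsely measured, not unmeasured.

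The size is uncertain. In the illustration, the grade costs about 10 to 50 percentage points of power against a direct length change. That rests on a 13 mm root, mean losses of 1.0 and 1.8 mm, SD 0.7, 15 completers per arm and error-free readings, none of which the protocol gives for this outcome. Reading error would lower the mm figure, and could also blur the grade. The direction does not depend on those exact values: a wide grade 2 hides differences within it.

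This is a secondary outcome. The primary comparison and the sample size are unaffected. The change is worth making because it is cheap and the outcome is a harm.

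**What to change.** In III) A], secondary outcome 3:

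1. Measure the root length of each anterior tooth in mm on the T0 and T1 CBCTs, with the landmarks stated.
2. Use the T0–T1 change in root length, in mm and as a percentage of T0 length, as the measure of root resorption during retraction.
3. Keep the 0–4 grade as a descriptive score. State that T0 length is the reference for loss at T1, and give a percentage limit between grades 2 and 3.
4. Make the reference number for the index agree with the outcome table.

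No new scan or staff is needed. The protocol already has landmarks read in mm on these two scans for anchorage loss. If the six upper anterior teeth are read in all 30 patients, this is 6 × 2 × 30 = 360 length readings, or 720 if both assessors read every tooth. The downside is that reading time.

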## **B] Data management:**

A colleague outside the research team will enter the data and organize it in excel sheets in the computer of the Orthodontics and Dentofacial Orthopedics department. Data will include all photographs, models, radiographs and filled questionnaire.

## **C] Statistical Analysis:**

- The principle investigator will be responsible for the extraction of the required data from the CBCT taken before and after retraction as well as the study models taken at every follow up visit. The data will be sent to a specialized statistician.
- The specialized statistician will be responsible for the statistical analysis of the study by:
  1. Presenting the data as mean, standard deviation (SD) and Standard error (SE) values.
  2. Using Paired t-test to compare between the friction and the frictionless group of retraction as well as to compare between the pre-and post -treatment data for each group.
  3. Using Anova test to determine the rate of anterior segment retraction.
  4. Statistically evaluate the patient acceptance for both techniques.
- For this study, the specialized statistician will use IBM11 SPSS12 Statistics Version 20 for Windows to perform the required statistics.
- The significance level will be  $P \leq 0.05$ . Highly significant variables are detected when P value is less than 0.01.

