### **Outcome measure:**

	Outcome Name	Measuring Tool	Measuring Unit
Primary Outcome	Anchorage loss	CBCT	

- Linear measurement in mm

Angular measurement in degrees

Secondary Outcome	Rate of space closure	Digital scanned Dental Model	

- Scanned digital models in (mm)

○ Models taken every month

○ Analysed using 3 Shape Software

	Pain	Pain scoring sheets given to patients	VAS scoring from 1-10 (Fig 1)

	Root resorption	CBCT	Scoring system of Levander and Malmgren[39] (5 grades classification)
	Torque of anterior teeth	CBCT	Degrees
	Tip of anterior teeth	CBCT	Degrees
	Vertical position	Digital scanned Dental Model	Mm
	1 st Permanent Molar rotation	Digital scanned Dental Model	Degrees

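### The 0–4 root-resorption grade falls under a mean, SD and SE presentation and a t-test, with no counts per grade, so severe cases can disappear from the results

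*Protocol*

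**What the plan says.** The Outcome measure table lists root resorption as a secondary outcome measured on CBCT, with the unit given as a "5 grades classification". Section III A], under Secondary outcomes, describes a scoring system "that classifies it into 5 grades: 0, no root resorption; 1, mild resorption" and so on up to the top category, "and 4, extreme resorption, with loss of more than one third of the root length". Section I D] Outcomes words the same item as a matter of presence: "rate of space closure, presence of any root resorption and pain associated". The Rationale section names root resorption among the adverse effects of uncontrolled tooth movement.

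Section III C] Statistical Analysis lists four tasks for the statistician:

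- the presentation: "Presenting the data as mean, standard deviation (SD) and Standard error (SE) values";
- the comparison of arms: "Using Paired t-test to compare between the friction and the frictionless group of retraction", with the same test for pre against post within each arm;
- the rate: "Using Anova test to determine the rate of anterior segment retraction";
- acceptance: "Statistically evaluate the patient acceptance for both techniques", with no method named.

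The section names no frequency table, proportion, ordinal method or rank method for any outcome. Kappa appears only under Assessors Reliability, for agreement between examiners.

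**The concern.** The grades are ordered categories and the distances between them are not equal. Grade 1 is a root of normal length with an irregular outline. Grade 3 is a loss of nearly a third of the root, and grade 4 a loss of more than a third. Averaging the codes 0 to 4 treats the step from nothing to a contour change as equal to the step across one third of root length. A mean of 0.8 could describe an arm in which almost everyone has a trivial change, or one in which most patients have none and a few have lost much of a root.

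That distinction matters most for an outcome that the protocol itself treats as a possible harm. If the stated rule is followed, the report would contain no figure from which a reader could tell how many patients in each arm had severe or extreme resorption.

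**Working it through.** **The plan's own figure.** The protocol gives no expected grade distribution and no power figure for root resorption. Its only calculation (section I F]) is for a continuous response with SD 0.76, difference 1.0, alpha 0.05 (taken as two-sided) and power 0.80:

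n = 2 × 0.76² × (1.960 + 0.842)² / 1.0² ≈ 9.07, rounded up to 10 per group.

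This reproduces the stated 10. It has no bearing on the grade except to fix the scale: 10 evaluable and 15 recruited per group.

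**Constructed example, 15 per arm.** The counts are an illustration, not a forecast.

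| Grade | 0 | 1 | 2 | 3 | 4 |
|---|---|---|---|---|---|
| Arm X | 12 | 0 | 0 | 0 | 3 |
| Arm Y | 3 | 12 | 0 | 0 | 0 |

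*What the stated presentation would show*

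- Mean X = (12×0 + 3×4)/15 = 0.8. Mean Y = (3×0 + 12×1)/15 = 0.8.
- SD X = √[(12×0.8² + 3×3.2²)/14] = √(38.4/14) = 1.66. SD Y = √[(12×0.2² + 3×0.8²)/14] = √(2.4/14) = 0.41.
- SE = SD/√15, which is 0.43 and 0.11.
- Unpaired t = (0.8 − 0.8)/SE of the difference = 0, so P = 1.0.
- Paired t, the test the protocol names: the mean of the paired differences equals the difference of the means, which is 0 however patients are paired. Again t = 0 and P = 1.0.

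*What it would not show*

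- Grade 4: 3/15 (20%) in X, 0/15 in Y.
- Any resorption (grade 1 or above): 3/15 (20%) in X, 12/15 (80%) in Y.

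**Whether a rank test alone would repair this.** In the pooled 30 patients, the 15 at grade 0 share rank 8, the 12 at grade 1 share rank 21.5, and the 3 at grade 4 share rank 29.

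- Mean rank X = (12×8 + 3×29)/15 = 183/15 = 12.2.
- Mean rank Y = (3×8 + 12×21.5)/15 = 282/15 = 18.8.
- The Mann-Whitney P-value is 0.024, in the direction of less resorption in X, the arm with all three extreme cases.

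A rank test answers a question about the overall ordering. It does not detect the severe cases here, so the counts are the essential part of the remedy.

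**A second example.** All 15 patients at grade 1 are compared with 11 at grade 0, 1 at grade 3 and 3 at grade 4. The second mean is (3 + 12)/15 = 1.0, equal to the first, and the t-test P is 1.00. Grades 3–4 occur in 0/15 against 4/15.

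**The case against.** **The section is generic.** It has four lines and never mentions root resorption. The presence wording in section I D] hints at a proportion, and outcome-specific methods are often left to a statistical analysis plan, which is not at hand. This has some force. But the protocol is not silent: it states a presentation and a group comparison without exception, and anyone following it would average the grades. A presence proportion is not provided for either, and in the first example it would be 20% against 80%, which also hides the three extreme cases.

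**The SDs would differ visibly** (1.66 against 0.41). They would, but an SD does not say how many patients reached grade 4.

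**No significant difference in severe cases was missed.** Fisher's exact test on 3/15 against 0/15 gives P = 0.22, and on 4/15 against 0/15 gives P = 0.10. This stands. The fault lies in what is reported, not in a lost significant result.

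**A reader might infer that the t-test loses power in general on this outcome.** The documents give no grade distribution from which to show that, and assumed ones do not bear it out. Simulations used 15 per arm, proportional odds, odds ratios of 3, 5 and 8, and 10,000 trials per setting:

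| Assumed % at grades 0–4 | Unpaired t, power % | Mann-Whitney, power % |
|---|---|---|
| 50/30/12/6/2 | 36/65/86 | 35/64/85 |
| 30/35/20/10/5 | 36/66/87 | 35/65/86 |
| 70/20/5/3/2 | 29/56/80 | 31/60/82 |

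The tests stay within about 4 points, and the rank test is slightly lower in two of the three cases. A large gap (0.34 against 0.67) arises with chosen crossing distributions of .75/.15/.02/.02/.06 and .25/.60/.13/.01/.01. There, however, essentially every significant rank result favours the arm with 6% rather than 1% extreme cases, so it is no evidence of better detection of harm.

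**A reader might also infer that every outcome goes to a t-test.** The section does not say so: the retraction rate goes to ANOVA, and patient acceptance has no named test.

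**Conclusion.** The point holds in a limited form. Followed as written, the Statistical Analysis section summarises an unequally spaced 0–4 grade by mean, SD and SE and compares arms by a t-test, with nothing that shows how many patients reached each grade. Equal means can then coexist with 3/15 against 0/15 patients at grade 4. The arithmetic of the examples is exact, but their counts are invented, and how often such a pattern would occur cannot be judged from the protocol.

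The conclusion rests on reading the stated presentation as covering all outcomes not treated separately, which is the plain reading. It does not depend on whether the t-test is paired or unpaired. The choice of a paired test for two independent parallel groups is a separate matter. The point is minor: it concerns the clarity of one secondary outcome and does not touch the primary analysis.

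**What to change.** In section III C], add a rule for root resorption:

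- Report the number and percentage of patients at each grade, by arm, using each patient's worst grade at T1.
- Report the number of patients at grades 3–4, by arm.
- Make any formal comparison with an ordinal or rank method for independent groups, exact where counts are sparse, and interpret it only beside the counts. A proportional-odds model would not suit distributions that cross.
- Keep mean and SD for outcomes measured in millimetres and degrees.

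The cost is a few lines of text, with no extra patients, visits or imaging. The one thing given up is a mean difference for this outcome.

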## **Study design:**

This is a randomized clinical trial with two arms parallel group, and 1:1 allocation ratio. In one group, frictionless mechanics will be applied during “En-masse retraction” while the other will receive frictional mechanics during retraction. The anchorage loss will then be compared between both interventions.

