## **F] Sample size calculation:**

Our sample size calculation is based on a previous study comparing the effect of friction and frictionless mechanics. Using PS software output, we are planning a study of a continuous response variable from independent Group I and Group II subjects with 1 Group I(s) per Group II subject. In a previous study the response within each subject group was normally distributed with standard deviation 0.76. If the true difference in the Group II and Group I means is 1.0, we will need to study 10 Group II subjects and 10 Group I subjects to be able to reject the null hypothesis that the population means of the Group II and Group I are equal with probability (power) 0.8. The Type I error probability associated with this test of this null hypothesis is 0.05. Considering drop out a sample size 15 per group is appropriate.

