## **II) Assignment of interventions:**

### **A] Sequence generation:**

The supervisor of the study will apply Computer generated random numbers to randomly assign patients to group A (Frictionless) or B (friction) using Microsoft Office Excel 2007 sheet. The patient numbers will be written in the first column, and the supervisor will select function RAND()to generate the randomization number in the second column. These numbers will be sorted according to the randomization number so the first column numbers will be randomly distributed.

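### The friction versus frictionless comparison is assigned a paired t-test, but the arms are independent parallel groups with no pairs

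*Protocol*

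**What the plan says.** Protocol, Statistical Analysis, item 2, gives the test for the comparison of the two techniques: "Using Paired t-test to compare between the friction and the frictionless group of retraction". The same sentence goes on to give the paired t-test a second use, pre- versus post-treatment within each group. The only other test named in that section is ANOVA, in item 3, for the rate of retraction.

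The rest of the protocol describes unpaired groups:

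- Study design: "This is a randomized clinical trial with two arms parallel group, and 1:1 allocation ratio".
- Sample size calculation: "we are planning a study of a continuous response variable from independent Group I and Group II subjects".
- Sequence generation: "Computer generated random numbers to randomly assign patients to group A (Frictionless) or B (friction", by sorting on a random number. Matching, blocking in pairs and split-mouth allocation are not mentioned there or in the concealment and implementation sections.
- Outcomes: "All outcomes will be assessed as the difference between T0 at the start of retraction and T1 after complete space closure". Each patient's change is therefore observed under one technique only.

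**The concern.** A paired t-test needs a defined link between each observation in one arm and one observation in the other. Here there is none, so an analyst who follows item 2 has to invent one. In practice it would be the row order of the data file. The Data management section says only that a colleague will organise the data in spreadsheets and fixes no order.

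Two things are at stake. The primary p-value is not uniquely defined: re-sorting the same data can move it across 0.05. In addition, the test cannot use every completer when the arms end with different numbers, which is likely in a trial that plans for dropout.

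This is not a detail left for a statistical analysis plan. The protocol names a test, and the test does not fit its own design. A later plan would have to repeat the error or contradict the protocol.

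**Working it through.** **Inputs.** From the protocol's sample size section: difference in means 1.0, within-group SD 0.76, alpha 0.05, power 0.8, 10 per group, raised to 15 for dropout. Two-sided testing is assumed, because the section does not state it. No dropout rate is given, so 10%, 20% and 33% are assumptions; the last is what the inflation implies, 1 − 10/15.

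**Step 1. Reproduce the protocol's figure.** For independent groups, two-sided:

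n = 2 × (1.960 + 0.842)² × 0.76² / 1.0² ≈ 9.07, rounded up to 10 per group.

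This matches. A one-sided calculation gives 8. A paired calculation that takes 0.76 as the SD of the differences gives 7 pairs. Of these, only the independent-groups, two-sided calculation gives 10.

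**Step 2. Power with complete data (noncentral t).** With uncorrelated arms, both tests have noncentrality 1.0 / (0.76 × √(2/n)), and only the degrees of freedom differ: 2n − 2 for the independent test and n − 1 for the paired test.

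| n per arm | Noncentrality | Independent | Paired |
|---|---|---|---|
| 10 | 2.94 | 79.5% (18 df) | 74.5% (9 df) |
| 15 | 3.60 | 93.5% (28 df) | 91.7% (14 df) |

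**Step 3. Why row order matters.** The mean difference is the same for every pairing. The variance of the differences is not: s_D² = s_A² + s_B² − 2·r·s_A·s_B, where r is the chance correlation created by the listing. With equal SDs, t_paired = t_independent / √(1 − r).

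Two simulated data sets, each with SD exactly 0.76 per arm and re-paired at random 5,000 times, illustrate this:

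- *15 per arm, observed difference 0.6.* Independent t = 0.6 / (0.76 × √(2/15)) = 2.16, p = 0.039. The paired test (critical value 2.145 on 14 df) is significant when r is at least 1 − (2.162/2.145)² ≈ −0.016, so in about half of orderings. Across re-pairings p ran from 0.0002 to 0.13, with 51% at or below 0.05.
- *10 per arm, observed difference 0.7.* Independent t = 2.06, p = 0.054. The paired test (critical value 2.262 on 9 df) needs r of at least 1 − (2.060/2.262)² ≈ 0.17. Across re-pairings p ran from 0.0007 to 0.17, with 32% at or below 0.05.

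**Step 4. How often this matters.** In 1,500 simulated complete trials per cell with 300 random orders each, the share of trials with at least 5% of orders on each side of p = 0.05 was:

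| True difference | 10 per arm | 15 per arm |
|---|---|---|
| 1.0 (protocol) | 33% | 12% |
| 0.5 (assumed) | 36% | 34% |

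Repeat runs agreed within about 2 percentage points.

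**Step 5. Dropout.** 40,000 simulated trials per cell, starting from 15 per arm, difference 1.0, SD 0.76, dropout independent in each arm:

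| Assumed dropout | Independent | Paired, completers listed consecutively | Paired, rows with a missing partner deleted | Arms unequal |
|---|---|---|---|---|
| 10% | 91% | 86% | 83% | 75% |
| 20% | 86% | 79% | 71% | 82% |
| 33% | 78% | 67% | 50% | 85% |

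Mean numbers of usable pairs were 12.9, 11.1 and 9.0 for the consecutive listing, and 12.2, 9.6 and 6.7 with row deletion. Even with consecutive listing, about 1.3, 1.7 and 2.0 completers are thrown away on average.

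**Step 6. Type I error.** With a true difference of zero, the paired test rejected in 4.9% to 5.2% of trials in every scenario.

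**The case against.** The strongest counter-argument is that this is a drafting slip with little effect. At the planned 15 per arm with complete data, power falls by less than 2 points and type I error is unaffected. The 50% figure needs one-third dropout and a row-deletion layout that the protocol does not describe, and the 0.5 difference is not a protocol value. A statistician is to run the analysis and might use the right test anyway. All of this is fair about size, and the worst cell should not be read as the expected case. It does not rescue the text: the sentence applies the paired test to the between-group comparison explicitly and first, so it cannot be read as meaning pre/post only. A hope that someone will depart from the protocol is no defence of it.

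Two limits also stand. Anchorage loss is listed in both millimetres and degrees, so correcting the test does not by itself produce a single primary p-value; that is a separate question. Retraction rate already has its own test in item 3, so a correction to item 2 should not give it a second one.

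**Conclusion.** The concern holds and should be corrected before analysis. The only between-arm test named for the primary outcome does not fit the design, contradicts the basis of the sample size, and leaves the result dependent on an arbitrary listing.

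On the protocol's own difference and SD, the cost with complete data is about 5 points of power at 10 per arm and about 2 points at 15. About one simulated trial in three at 10 per arm, and one in eight at 15, is materially open to a change of conclusion by re-sorting. Under assumed dropout of 10% to 33%, the paired test loses roughly 5 to 11 points of power if completers are listed consecutively, and more if incomplete rows are deleted.

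These figures assume normal outcomes, equal SDs, two-sided testing, dropout unrelated to outcome, and a row order unrelated to outcome. The type I error result depends on that last condition.

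**What to change.** Replace item 2 with wording such as:

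> The T0–T1 change in anchorage loss is compared between the two arms with an independent-samples t-test. The same test is used for other continuous outcomes assessed as a T0–T1 change, except retraction rate, which is covered by item 3. The paired t-test is used only for pre/post change within each arm.

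The independent-samples t-test should be the single named between-arm test for anchorage loss. If an ANCOVA adjusting for the T0 value is wanted, label it as supporting only. The five-grade root resorption score is ordinal and should not be read as covered by this item.

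The cost is one sentence through the protocol's amendment procedure. The sample size stands, since 10 per group was derived for independent groups. The named software includes the test, and no patients, visits or measurements change.
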